 - ii. **At least one** of the problems must be: symptom 1 (feeling depressed) or symptom 2 (losing interest or pleasure), **and**
 - iii. The participant indicates '**yes**' to the question: *Did these problems interfere with your life or activities a lot?*
2. Behavioral activation scale score (BA)
3. Social support (due to the highly skewed nature of this outcome, we dichotomized it into ≥ 4 versus <4).
4. Mood regulation
5. Decentering
6. Mental health service utilization (i.e., an indicator for whether participants are enrolled in therapy with a counselor and/or currently taking antidepressants). This outcome may be explored in greater detail in a separate paper; however, we plan to examine the difference between arms controlling for baseline mental health service utilization.

Tertiary Outcomes (the following will be explored in a separate paper from the primary results)

1. Pleasant activities
2. Perceived stress
3. Parental cognitions and conduct toward the infant scale
4. Dyadic adjustment scale
5. Flourishing scale
6. Prenatal health behaviors

The outcomes above are tied to validated scales with specific scoring requirements. The scoring instructions will be followed and analyses will proceed on the final, scored variables. In addition, we plan to summarize '**dosage**' of intervention in the active intervention arms as the number of sessions attended (out of six possible). We will also summarize the number of participants that were '**compliant**', which is defined as attending **at least four of the six sessions**.

Demographics and Baseline Assessments

The following are specific demographic/baseline assessments of interest for analyses. Primary analyses will adjust for these covariates as we anticipate they will influence outcome. We plan to report both adjusted and unadjusted intervention effect estimates:

1. Race/ethnicity (at the participant level): minority vs. not belonging to a minority category.
2. Whether participant is a first-time mother (i.e., current number of children = 0 at baseline).
3. Currently at risk for depressive episode (i.e., those NOT meeting criteria for MDE at baseline).

4. Primary language of intervention receipt (for MH and HV arms) or primary language in which the participant completed assessments (for control arm).
5. Education: at least some college vs. less than college.

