4. Of those that meet acceptable levels of imbalance, we randomly select one allocation for use in the current study.

We chose the p-value corresponding to the Kruskal-Wallis test (nonparametric version of an Analysis of Variance [ANOVA]) as our criterion for 'balance' in step #3 above. If the p-value for each of the three variables is larger than 0.30 for a given simulated allocation scheme, that particular allocation is deemed 'acceptable'. This criterion is adapted from the 'Minimal Sufficient Balance' principle from Zhao et al. [3] in the individual sequential randomization literature.

In the current study, randomization occurred in three waves for logistical purposes. The first included 14 sites (2 C:6 HV:6 MH); the second included 19 sites (4 C:7 MH:8 HV); allocation ratio was slightly off in this wave to account for dropout sites); and the third wave included 12 sites (1 C:6 MH:5 HV). Thus, we randomized a total of 45 sites in three waves; randomization of 42 sites was the study goal, reflected in our approved research plan. However, to account for site dropping out in the meantime, we adapted the algorithm to increase the number of sites randomized and also to allow for slightly discrepant allocation ratios than the planned 1:3:3 within each wave.

After randomization, eight programs dropped out, thereby yielding a total of 37 study sites contributing data for analyses. Data collected from all study participants will be used in the analysis. Among the 37 active study sites, 16 HV programs received the MB intervention delivered by mental health professionals, 15 received MB intervention delivered by HV paraprofessionals, and six programs serve as control sites. As an aside, 29 intervention sites ended up implementing at least one cohort (15 MH, 14 HV).

Statistical Methods

Descriptive statistics will summarize baseline characteristics (both site-level and participant-level) overall and by arm. As appropriate, mean \pm standard deviation (or median [inner quartile range]) will be used in cases of skewed or non-normal empirical distributions) and frequency (proportions) will summarize continuous and categorical data, respectively. Analyses will employ normal theory methodology as appropriate, and in cases of violations of assumptions, transformations and/or nonparametric analyses may be utilized.

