Analyses will proceed at the participant level. Primary analyses for QIDS-SR16 score at 24 weeks postpartum will involve all the participants in the study contributing data at this time point. Primary analyses will involve a linear mixed model for continuous outcome with independent fixed effect variables of baseline QIDS-SR16, study arm (three-level factor), and the baseline covariates listed above. We will report both covariate-adjusted and unadjusted estimates for intervention effect. Secondary analysis will be performed on those participants considered at risk at baseline (i.e., excluding the participants who do not meet the criteria for MDE as defined above). We plan to account for clustering effects via inclusion of a random site effect, which will allow for distinction of between and within-site variance. We will also explore inclusion of a random 'facilitator' effect as it is possible participants exposed to the same facilitator may have correlated responses. Intra-cluster correlation coefficients will be estimated via variance components estimates.

Intervention effect will first be evaluated via the adjusted Wald type III test for significant study arm effect at the 5% level of significance. If arm is significant at the 5% level, analyses evaluating the **superiority (Aim #1)** of HV-led intervention vs. control will proceed with Tukey's correction for multiple pairwise hypothesis tests. Assuming the Tukey-adjusted p-value for this comparison falls below the 5% level of significance in favor of the HV-led arm, **non-inferiority (Aim #2)** will further be assessed (using Tukey's correction) via pairwise comparison of adjusted 24-month QIDS in HV-led vs. MH-led arms. Figure 1 below depicts the margin and zone of non-inferiority for this comparison.

[figure not shown]

Figure 1. Margin of Non-inferiority (NI)

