The double-sided arrows represent 95% confidence intervals for the model-estimated adjusted mean 24-week difference in QIDS-SR16 score. Note that higher score signifies more depressive symptoms; thus if the estimated difference (HV minus MH score) is larger than zero, the HV arm has on average worse depressive symptoms. Since the pre-specified margin of non-inferiority is two units on the QIDS-SR16 scale, we will claim non-inferiority if the upper limit of the adjusted 95% confidence interval for the HV-led arm minus the MH-led arm comparison remains below two. The red arrows indicate scenarios in which we cannot claim non-inferiority and the blue arrows indicate scenarios in which the criterion for non-inferiority is met.

Using the same analytic approach, we will explore the addition of covariate-by-arm interaction terms in the aforementioned model or a three-way covariate-by-arm-by-time interaction term in the longitudinal modelling in order to explore whether effectiveness of intervention varies by patient characteristics (Aim #3). The covariates to be explored include: race/ethnicity, first-time mother, language, education, and use of mental health services at baseline. These analyses are more exploratory in nature, and thus power/sample size considerations do not focus on interaction effects. As a result, we anticipate evaluating interaction effects at the 10% level of significance without adjustment for multiple hypothesis tests. Qualitative data analysis methods will evaluate feasibility and acceptability of MB in each setting (Aim #4), and the details of these analyses will be specified elsewhere.

Additional analyses surrounding Aims #1-#3 will employ longitudinal methods, utilizing all study data at all time points (i.e., inclusion of a fixed study time point effect). Secondary outcomes will all be analyzed in this fashion with the exception being binary response variables (e.g., depression onset). In these cases, appropriate link and distributional assumptions (logit, binomial, respectively) will be specified. For the participants receiving active intervention (either HV-led or MH-led Mothers and Babies), we will examine a 'dose' variable in relation to outcomes. This dose variable will be defined as the number of sessions (out of six possible) attended for an individual participant.

Analytic Dataset

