Analyses will be conducted on the modified intent-to-treat (mITT) dataset whereby all participants randomized with data at the 24-week time point will be analyzed according to arm to which they were allocated. We will further perform a sensitivity analysis on the 'as treated' dataset. Those in either active intervention arm will be considered 'treated' if they attend at least four out of the six sessions required for the Mothers and Babies course. For participants with missing data at baseline and non-missing data at follow-up, we plan to impute mean baseline values from the participants' follow-up in order to allow for inclusion in analyses.

Power and sample size considerations allowed for some missing data and, as specified in our approved research plan, we have allowed for up to two clusters to drop out of each arm; however, in the event of large amounts of missing data (i.e., more than 15%), multiple imputation analyses will be explored. We will examine rates of missing data for all variables and determine whether the rates vary by participant characteristics, HV program location, or intervention arm. These summarizations will inform potential biases resulting from missing data. The mixed effects models planned for analysis are generally robust for unbalanced data across study time points. We plan to apply multiple imputation in order to account for missing data; we will impute at least five datasets to generate an estimated average intervention effect. These analyses will again serve as sensitivity analyses to the previously outlined analyses. For participants missing individual items on a particular assessment, we plan to randomly sample from the non-missing empirical distribution for that item. We anticipate less than 5% of participants that would require this imputation of individual items. Again, in the event of large amounts of missing individual items, we will explore multiple imputation methods.

Power and Sample Size Considerations

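### The language covariate in the primary adjusted model is defined by intervention receipt in the two Mothers and Babies arms but by assessment language in control, with no fallback for women who attended no session

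*SAP*

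**What the plan says.** Item 4 of the adjustment list in the SAP, Demographics and Baseline Assessments, is "Primary language of intervention receipt (for MH and HV arms) or primary language in which the participant completed assessments (for control arm"). Under Statistical Methods the primary linear mixed model takes "independent fixed effect variables of baseline QIDS-SR16, study arm (three-level factor), and the baseline covariates listed above", so item 4 is in it. Language also returns as an Aim 3 effect modifier: "The covariates to be explored include: race/ethnicity, first-time mother, language, education, and use of mental health services at baseline".

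On who is analysed:
- SAP, Analytic Dataset: "all participants randomized with data at the 24-week time point will be analyzed according to arm to which they were allocated". No attendance condition is attached.
- SAP, Randomization Methods: "Data collected from all study participants will be used in the analysis".
- Protocol 4.0, Participant Outreach and Contact: women are followed to 24 weeks postpartum whether or not they attend sessions.
- SAP, Randomization Methods, on sites: dropouts left the trial "yielding a total of 37 study sites contributing data for analyses", of which 16 are clinician-led (MH), 15 home-visitor-led (HV) and 6 control. The same section adds that "29 intervention sites ended up implementing at least one cohort (15 MH, 14 HV").

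On missing values, the Analytic Dataset section says "For participants with missing data at baseline and non-missing data at follow-up, we plan to impute mean baseline values" taken from the woman's own follow-up. Multiple imputation is described there as a sensitivity analysis.

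**The concern.** An adjustment covariate should mean the same thing in every arm and be fixed before treatment can influence it. This one does neither. Two consequences follow.

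1. **Mixed definition.** In the HV versus control contrast, the model equates delivery language in one arm with assessment language in the other. Any net disagreement between the two within the MB arms is carried into the adjusted treatment difference.

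2. **Undefined values.** A woman allocated to MB who attended no session has no language of receipt. If the gap were left to a software default, the fit would drop women from the MB arms only, contrary to the modified intention-to-treat rule.

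The model concerned supplies the overall arm test, the HV versus control superiority test and the non-inferiority (NI) limit for HV versus MH. An Aim 3 language-by-arm term would mix the two definitions as well.

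**Working it through.** **Is the gap real?** MB sites contributing data: 16 + 15 = 31. MB sites that ran a cohort: 15 + 14 = 29. The difference is 2 sites, one MH and one HV. Any woman analysed from these two has no language of receipt, and the same holds for a woman elsewhere who never attended.

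**Does another rule fill it?**
- Averaging a woman's follow-up values cannot produce a category that her follow-up surveys are not said to record.
- Sampling from the empirical distribution applies to single missing items on an assessment.
- Multiple imputation is not part of the primary analysis.
- The non-binding baseline table shell lists primary language for every arm but does not define it.

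**Is it a baseline variable?** Protocol 4.0 requires baseline data before the first MB group. Language of receipt, taken literally, is settled only once the course is delivered.

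**Size of the mixed-definition effect.** Assume language shifts QIDS by b points, given the other covariates, and that a net share d of MB women have a delivery language different from their assessment language. Mean recorded language in the MB arms then moves by d relative to control. The adjusted HV–control difference moves by (fitted language slope) × d, which is close to b × d because misrecording pulls the slope slightly below b. With arms in the ratio 6:16:15, language prevalence 20–50% and all disagreement in one direction:

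| b (assumed) | d = 1% | d = 5% | d = 10% |
|---|---|---|---|
| 1 point | 0.01 | 0.05 | 0.09 |
| 2 points | 0.02 | 0.09 | 0.18 |

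These are at the upper end. Reversing the direction of disagreement changes the sign and gives a similar or smaller size (0.07 for b = 1, d = 10%, prevalence 20%). Disagreement that is equal in both directions gives zero. HV–MH bias is essentially zero when d is the same in both MB arms.

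**Size of the missing-value effect, two no-cohort sites only.** Inputs from the SAP power section: SD 6, NI margin 2, ICC 0.01, alpha 0.05/3 (used two-sided), 23 analysed women per site. A true difference of 0 is assumed.

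- Variance of a site mean: v(m) = 36 × [1 + 0.01(m − 1)]/m. So v(23) = 1.910, v(8) = 4.815, v(1) = 36.
- Variance of an arm mean: 1/Σ(1/v) over its sites. SE² is the sum over the two arms.
- Power: noncentral t with (number of sites − 2) degrees of freedom and noncentrality 2/SE.

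This method reproduces SAP Table 1 at ICC 0.01 (20 per site with 16 sites per arm, 22 with 15). It gives 93.3% for 16 + 16 sites of 23, in line with the SAP's claim of over 90%.

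With both no-cohort sites lost (15 + 14 sites, 27 df): SE = √(1.910/15 + 1.910/14) = 0.514, power 90.2%. With them kept (16 + 15 sites, 29 df):

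| Women analysed at each no-cohort site (assumed) | Share of MB women affected | SE | NI power if kept | NI power if lost |
|---|---|---|---|---|
| 1 | 2/669 = 0.3% | 0.513 | 90.5% | 90.2% |
| 8 (one cohort) | 16/683 = 2.3% | 0.507 | 91.2% | 90.2% |
| 23 (ceiling) | 46/713 = 6.5% | 0.497 | 92.4% | 90.2% |

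In the HV arm, 8 of 14 × 23 + 8 = 330 women is 2.4%. Omitting them would move the HV mean by about 0.02 points for each point by which retained and omitted women differ. If the two sites have no 24-week data, the loss is zero.

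**Non-attenders at the other 29 sites.** The documents give no rate. Purely as an illustration, suppose 10%, 20% or 30% of the 23 women per site attended nothing and a complete-case fit dropped them as well as the two sites. NI power would then be about 87%, 83% or 78%.

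**The case against.** The strongest reply concerns weight. Every bias figure rests on assumed values, and the largest is 0.18 points against a meaningful difference of 5. Baseline QIDS, minority status and education are also in the model, so the remaining language effect may be well under a point. Symmetric disagreement cancels. The SAP plans no exclusion and says all women with 24-week data are analysed, so complete-case deletion would depart from the plan. The unadjusted estimate, also to be reported, does not use the covariate, and HV–MH uses one definition in both arms. All of this stands, and it is why the effect is called small.

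A second reply is that receipt may be meant loosely, as the language of the group a woman was allocated to. The SAP does describe 31 programs as having received MB when 29 ran a cohort, and the documents do not say how or when the variable is recorded. That reading would reduce the missing values, but a site with no cohort still has no group language on record, and the definition would still differ from control.

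A third is that delivery language matters for Aim 3, and that a stored completion language is not documented for MB women. The first part is fair and can be accommodated. On the second, the SAP already relies on assessment language for controls, and all clients complete the same English or Spanish surveys in REDCap (Protocol 4.0 and 8.0).

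**Conclusion.** The concern holds. The SAP states an arm-dependent definition for a covariate in its primary adjusted model, and that covariate has no value for some women the plan intends to analyse. No stated rule resolves this in the primary analysis.

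The expected effect on conclusions is small. It is 0.01 to 0.18 points on HV versus control under the assumed b and d. From the two no-cohort sites, it is at most about 2 percentage points of NI power, and only if their women were dropped by default. The contribution of non-attenders elsewhere cannot be sized from the documents. The direction of any bias is unknown. The definition should be corrected because it sits in the confirmatory model and leaves the handling of these women to an analyst's choice or a software default.

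**What to change.** Rewrite item 4 so that language in all three arms is the language in which the woman completed her baseline survey (English or Spanish), or the language of consent if that is missing. Consent precedes the baseline survey, so this is a true baseline variable with one meaning in every arm.

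Language of group delivery can stay as a descriptive variable, or as an exploratory Aim 3 modifier within the MB arms, with baseline survey language substituted for women who attended no session.

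The cost is one SAP line, documented under the SAP's own version control. No new data should be needed, since consent and surveys are offered in English or Spanish to clients in every arm. The team should confirm that the completion language is stored for all arms before the database is locked.

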To safeguard confidentiality and anonymity, all data collection instruments will identify participants only by study ID number. Logs linking information to study numbers will be kept locked in a file cabinet in the Project Manager's office. Data analysis staff will not have access to identifying information. We will inform participants of the areas to be covered in the surveys prior to their administration. Study participants will be told that if they experience any discomfort while participating in the data collection procedures they can ask to be removed from the study. Also,

participants will be told that they do not have to respond to any questions that make them feel uncomfortable. Individuals will be told that their refusal to answer any question will not jeopardize their relationship with their home visiting program and will not affect their receipt of home visiting services.

We believe that the use of the REDCAP data collection system will allow us to collect high quality data from all study participants and will not require the need for additional procedures to monitor data quality.

Power Analysis: For our **superiority analyses** (Aim 1) comparing MB led by home visitors vs. usual care, we have assumed a standard deviation of ~6.0 points on the QIDS-16—our measure of depressive symptoms. We anticipate over 95% power to detect a five-point difference between study arms (HV- led MB vs. usual care) with ICC's up to .01; thus, the planned sample size and anticipated dropout rate provide adequate power to detect meaningful differences across arms for our superiority analysis. We have also conducted power and sample size calculations that take into consideration the possible loss of clusters (i.e., HV programs) within each study arm. Even with a loss of two clusters implementing MB and one cluster providing usual care, we will have over 90% power to detect a five-point difference between study arms on the QIDS-16. Previous published prevalence data and previous MB data illustrate a 15% reduction in incidence of depressive episodes, and again, we anticipate minimal ICC. We expect power >95% to detect an absolute risk reduction of 15% in the intervention arm for ICCs no larger than 0.01.

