We initially planned to conservatively enroll 42 sites (six controls, 18 HV-led, 18 MH-led) with a target enrollment of 40 participants per site (1680 total participants). As in any cluster-randomized trial, power and sample size considerations depend heavily on intra-cluster correlation coefficient (ICC) estimates. In general, it is recommended that these calculations account for anticipated ICC as failure to do so in the design phase and lead to an increase in type II error (i.e., result in underpowered studies) [4, 5]. Without previous knowledge of ICC(s) in this population with respect to our primary outcome, we explored a range of ICCs (0.001 to 0.05). Power calculations assume a standard deviation in primary outcome of approximately six points (on the QIDS-SR16), with a meaningful difference corresponding to five points on average across arms. Thus, for the superiority aim, we calculated power based on the average ability to detect at least a five-point mean difference between control sites and HV-led sites. Power calculations assumed a $5\%/3 = 1.7\%$ level of significance in order to account for three pairwise comparisons. This is an approach that we deem conservative as this mirrors the Bonferroni correction for multiple hypothesis tests.

We have 38 active sites: six control, 16 paraprofessional home visitor-led sites, and 16 MHP-led sites. We plan to recruit an average of 27 participants per site, allowing for up to 15% attrition (i.e., 23 participants on average for analyses). These assumptions allow for more than 95% power to detect a mean difference of five points in QIDS-SR16 across arms for an ICC of 0.01. Even if one of the six sites drops out, and if ICC is as large as 0.05 (which we deem unlikely), we still anticipate over 85% power for analyses addressing the efficacy aim (Aim #1).

Power for the NI aim will require ability to detect a smaller (margin of NI of two points) mean difference across arms. We anticipate over 90% power to detect a margin of NI of two points on the QIDS-SR16 scale if we assume an ICC of 0.01 and 16 sites in each of the intervention arms with 23 participants for analyses, on average, per site. This allows for up to 15% attrition overall. We anticipate some sites to be over/underperforming and thus unequal representation per site is inevitable. Our hope is that the precautions taken with respect to the randomization algorithm that

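### Site allocation was constrained on three site variables that the primary model omits; with eight of 45 sites lost, the adjusted analysis should include them

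*SAP*

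**What the plan says.** The SAP's Randomization Methods section names three site-level variables to be balanced: percent non-White clients, yearly client volume and population density. An allocation was acceptable if the Kruskal-Wallis p-value exceeded 0.30 for each. Allocation ran in three waves: "The first included 14 sites (2 C:6 HV:6 MH); the second included 19 sites (4 C:7 MH:8 HV") and "the third wave included 12 sites (1 C:6 MH:5 HV"). Losses followed: "After randomization, eight programs dropped out, thereby yielding a total of 37 study sites contributing data for analyses". By arm, "16 HV programs received the MB intervention delivered by mental health professionals, 15 received MB intervention delivered by HV paraprofessionals, and six programs serve" as controls. The SAP explains that 45 sites rather than 42 were randomised to make up for dropout.

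Under Statistical Methods, the primary linear mixed model has "independent fixed effect variables of baseline QIDS-SR16, study arm (three-level factor), and the baseline covariates listed above", plus a random site effect. The list referred to, under Demographics and Baseline Assessments, has six items, all at participant level.

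On cluster loss, the SAP's Analytic Dataset section says "we have allowed for up to two clusters to drop out of each arm". The protocol's Power Analysis (section 14.0) makes two allowances. For superiority it reads "Even with a loss of two clusters implementing MB and one cluster providing usual care"; for non-inferiority it allows up to two lost clusters in each arm compared.

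**The concern.** The design team thought these three variables important enough to restrict the allocation on them, yet the model that estimates the intervention effect ignores them. The SAP gives no reason. Two consequences follow.

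First, the analysis does not match the design. The random site effect treats the contribution of these variables as unrestricted between-site noise, although allocation restricted it.

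Second, balance was set on the sites as randomised, and eight of them do not contribute data. If withdrawal was related to volume, location or client mix, and those relate to 24-week QIDS-SR16, the HV-control and HV-MH contrasts would carry an imbalance. A random site effect puts residual between-site variance into the standard error, but it does not correct a difference between arms in site characteristics. The SAP states no re-check of its balance rule on the 37 sites and no comparison of withdrawn with retained sites.

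**Working it through.** **1. Site counts (SAP, Randomization Methods; planned numbers from Power and Sample Size Considerations)**

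| Arm | Randomised | Retained | Lost | Planned | Short of plan |
|---|---|---|---|---|---|
| Control | 2+4+1 = 7 | 6 | 1 (14.3%) | 6 | 0 |
| HV | 6+8+5 = 19 | 15 | 4 (21.1%) | 18 | 3 |
| MH | 6+7+6 = 19 | 16 | 3 (15.8%) | 18 | 2 |
| Total | 45 | 37 | 8 (17.8%) | 42 | 5 |

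The SAP's own arithmetic, 45 − 8 = 37, is right.

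**2. Is the loss uneven?** Proportional loss would be 8 × 7/45 = 1.24 in control and 8 × 19/45 = 3.38 in each MB arm, against 1, 4 (HV) and 3 (MH) observed. An exact test of loss by arm gives p = 1.0.

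**3. Against the allowance.** Measured from the planned 18, HV is three short and exceeds two by one site. MH is two short, within it. Control is not short. Only if losses are counted from the 19 randomised does MH (3) also exceed two.

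**4. Power.** A two-mean comparison with design effect 1 + (m − 1) × ICC, SD 6, difference 2, two-sided alpha 0.017 and a noncentral t with 2(k − 1) degrees of freedom for k sites per arm reproduces all 12 entries for participants analysed per site in SAP Table 1. With 23 per site and ICC 0.01, the same method (degrees of freedom: sites in the two arms minus 2) gives about 93% power for 16 + 16 sites and about 92% for the actual 15 HV + 16 MH. Table 1 already covers 15 sites per arm (22 needed per site, 23 expected).

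**5. Balance after loss (simulation).** Assumptions: three independent normal site variables; the p > 0.30 rule applied within each wave, which the SAP does not specify; then loss of 1 control, 4 HV and 3 MH sites.

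- The share of trials meeting the rule on all sites is about 75% with 45 sites, about 64% after random loss, and 58-59% if low-volume HV sites tend to leave.
- The SD of the HV-control imbalance goes from about 0.32 to 0.37-0.38 site-SD. Simple randomisation of 6 against 15 sites gives √(1/6 + 1/15) = 0.48.
- The 95th percentile of the absolute imbalance goes from about 0.63 to 0.76 site-SD for HV-control, and from 0.46 to 0.55 for HV-MH.
- If all 45 sites are instead allocated jointly to meet the rule, at least one variable fails it in about 34% of trials after random loss. This is about 53% if the four lost HV sites are the highest on one variable.

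**6. In QIDS points.** The documents give no slope, so 0.3 to 0.6 points per site-SD is assumed. The upper value is the whole between-site SD at ICC 0.01: √(0.01 × 6²) = 0.6.

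- Added by random loss, HV-control: (0.76 − 0.63) × 0.3 to 0.6 = 0.04 to 0.08.
- Added by random loss, HV-MH: (0.55 − 0.46) × 0.3 to 0.6 = 0.03 to 0.05.
- Systematic shift if low-volume HV sites tend to leave (about 0.2 site-SD in both contrasts): 0.2 × 0.3 to 0.6 = 0.06 to 0.12.

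The benchmarks are 5 points for HV-control (the stated meaningful difference) and 2 points for HV-MH (the non-inferiority margin).

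**7. Cost of adjustment.** Between-site degrees of freedom are 37 − 3 = 34 now and 34 − 3 = 31 with the three site variables.

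**The case against.** The strongest reply is that little harm is likely. Much of the gain from constrained allocation survives random loss (SD 0.37-0.38 against 0.48 for simple randomisation). Over-randomising to 45 sites was meant to offset dropout, and Table 1 anticipates 15 sites per arm. Participant-level minority status is already adjusted for and overlaps with percent non-White clients. Site-level baseline descriptives by arm are planned, as are missing-data rates by arm and program location. All of this stands and limits the size of the point. It does not explain why volume and density, which have no proxy in the model, are left out, and descriptive tables do not adjust an estimate.

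A second reply is that linear volume and density terms could have leverage with only six control sites, whereas the balance rule was rank-based. That is fair, and it affects how the terms should be entered.

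Four stronger readings are tempting but unsupported:
- A reader might infer differential dropout by arm. The counts are near proportional, and the SAP gives no reasons for withdrawal.
- A reader might infer that every arm went past the allowance. Against the planned sites, only HV did, by one.
- A reader might take the SAP sentence starting "Our hope is that the precautions taken with respect to the randomization algorithm that" as a claim that balance survives withdrawal. It concerns unequal recruitment per site.
- A reader might infer a loss of power. At ICC 0.01 it is about one percentage point for non-inferiority.

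**Conclusion.** The point holds as a mismatch between design and analysis, which site withdrawal makes more worth fixing. The primary model omits all three variables used to constrain allocation, and no balance check on the 37 retained sites is stated. Under the assumptions above, random loss adds less than about 0.1 QIDS points to the 95th percentile of either contrast, small beside 5 and 2 points. The selective-loss scenario gives a systematic shift of about 0.06 to 0.12 points. Both rest on independent site variables and an assumed slope whose upper value lets one variable explain all between-site variation at ICC 0.01; a larger ICC or more selective loss would raise them. The documents do not show that bias has occurred. This is an inexpensive improvement to the primary analysis and does not by itself undermine the trial's conclusions.

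**What to change.** - **SAP, Statistical Methods:** add percent non-White clients, yearly client volume and population density as site-level fixed effects in the primary adjusted model, log-transforming volume and density if skewed. All three were fixed before allocation, so adjusting for them adds no post-randomisation bias. The unadjusted estimate already planned stays as the comparison.
- **SAP, Randomization Methods:** say whether balance was judged within wave or cumulatively. Report the three variables by arm for the 45 randomised, 37 retained and eight withdrawn sites.
- **SAP, Analytic Dataset:** state that, against the planned 6 control, 18 MH and 18 HV sites, the shortfall is 0, 2 and 3, so HV exceeds the two-cluster allowance by one. Cite both protocol allowances: two MB clusters and one control for superiority, two per MB arm for non-inferiority.
- **Reconcile the site count:** Randomization Methods gives 37 active sites with 15 HV; Power and Sample Size Considerations gives 38 with 16 HV.

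The cost is three between-site degrees of freedom (34 to 31), some leverage risk with six control sites, and SAP wording. No new data are needed.
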